	reported adverse effects making it a potentially attractive alternative for
	individuals seeking pharmacological support to quit smoking (13). Despite
	The Smoke Free app (https://smokefreeapp.com/) is a widely used digital
	promising results, only limited research has directly compared cytisine with varenicline (e.g., (14)), particularly in the context of digital interventions and in the UK. The Smoke Free app (https://smokefreeapp.com/) is a widely used digital smoking cessation tool, with over 7.6 million downloads and around 60,000

new users each month, that provides users with personalised quit plans, behavioural support, progress tracking, and pharmacotherapy recommendations (15). Digital platforms like Smoke Free offer an accessible and cost-effective means of delivering smoking cessation interventions (16, 17), overcoming common barriers such as time constraints and financial limitations associated with traditional support services (18).

This study will leverage the Smoke Free app to conduct a randomised controlled trial (RCT), assigning participants to receive a digital recommendation for either cytisine or varenicline. By examining the effectiveness of these recommendations in a real-world digital setting, the trial will provide valuable insights into whether cytisine's natural plant-based appeal and potentially lower adverse-event profile translate to higher medication usage compared to varenicline, which could lead to higher overall quit rates given similar efficacy (8). In the context of the increasing use of digital health interventions, this study has the potential to inform future public health strategies aimed at reducing smoking prevalence through innovative, scalable, and cost-effective solutions.

Research questions

The primary research questions are:

- 1. Does a digital recommendation for cytisine or varenicline (intervention arms) compared to no recommendation (control arm) increase medication use (defined as percentage of participants in the intervention arms who use either varenicline or cytisine) at two months after enrolment among individuals using a stop smoking cessation app during their quit attempt?
- 2. Among participants who receive a digital medication recommendation, is there a difference in medication use between those recommended cytisine and those recommended varenicline at two months after enrolment?

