Participants in the varenicline arm will receive a digital recommendation and support to use varenicline during their quit attempt, along with information on varenicline's benefits and potential side-effects, instructions for proper use, and guidance on how to obtain the medication either free of charge or with the standard NHS prescription charge. They will also be advised to access the Smoke Free app using a unique link provided to participants in the varenicline arm, where they will receive smoking cessation behavioural support and advice on the benefits of using varenicline during their quit attempt. One day after randomisation, they will receive an email with similar information on varenicline's benefits and potential side-effects, instructions for proper use and guidance for obtaining the medication and a reminder to use the Smoke Free app for smoking cessation behavioural support.

Cytisine arm

Participants in the cytisine arm will receive a similar digital recommendation to use cytisine during their quit attempt, along with information on its benefits and potential side-effects, instructions for proper use and guidance on obtaining the medication either free of charge or with the standard NHS prescription charge. They will also be advised to access the Smoke Free app using a unique link provided to participants in the cytisine arm, where they will receive smoking cessation behavioural support and advice on the benefits of using cytisine during their quit attempt. One day after randomisation, they will receive an email with similar information on cytisine's benefits and potential side-effects, instructions for proper use and guidance for obtaining the medication and a reminder to use the Smoke Free app for smoking cessation behavioural support.

The Smoke Free app will be restricted for participants who enrol in the study, and they will only be able to access it through the unique link based on their group allocation. If participants opt out of the study, they will regain normal access to the Smoke Free app.

Measures

Outcomes

The primary outcome will be percentage of participants reporting medication use (varenicline or cytisine use) at the 2-month follow-up. We will also report percentage of participants reporting varenicline or cytisine use among those recommended one of them at the 2-month follow-up.

Secondary outcomes will be percentage of participants reporting:
(i) continuous abstinence for one month assessed at 2-month follow-up.

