(ii) biochemically-verified continuous smoking abstinence for six months assessed at the 7-month follow-up by a) group allocation (cytisine vs varenicline vs control) and b) by use of recommended medication among those in the intervention arms. Following the Russell Standard, self-reported abstinence will be measured as not having smoked more than five cigarettes for the entire 6-month period preceding the 7-month follow-up (20). Analyses will follow the intention-to-treat principle. This means that all

participants will be analysed in the groups to which they were originally assigned, regardless of whether they completed the study or adhered to the intervention. Multiple imputation will be used to account for missing outcome data (i.e., participants who will be lost to follow-up or did not provide outcome data). As a sensitivity analysis, missing data will be treated as no medication users (for medication use outcomes) and smokers (for smoking cessation outcomes) in the analysis. Self-reported abstinence will be biochemically verified by measuring participants' CO levels via a video call with a researcher. A CO monitor will be sent to participants who self-report abstinence at 7-month follow-up and those with a CO reading of less than 8 parts per million will be classified as abstinent (21, 22).

The baseline questionnaire will assess the following:

Participants' contact details: e-mail address, mobile phone number.

Baseline

Sociodemographic characteristics:

age,

sex (male, female, other),

education (any versus no post-16 qualifications),

financial status (live comfortably, meet needs with little left, just meet basic expenses, do not meet basic expenses (23)),

country of residence (England, Scotland, Wales, Northern Ireland), ethnicity (Asian or Asian British background, Black, Black British, Caribbean or African background, White background, mixed or multiple ethnic groups (e.g., White and Black African or White and Asian), other ethnic group).

Smoking related characteristics:

number of cigarettes smoked per day,

cigarette addiction (first cigarette within 5, 6-30, 31-60 or >60 minutes of waking),

urges to smoke (How much of the time have you felt the urge to smoke a cigarette in the past 24 hours? (not at all, a little of the time, some of the time, a lot of the time, almost all the time, all the time); How strong have the urges been? (no urges, slight, moderate, strong, very strong, extremely strong)(24, 25),

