Participants who report 6-month continuous abstinence at the 7-month follow-up will be asked to measure their CO levels to verify their abstinence. This will be conducted via a video call with a researcher, using a CO monitor provided by the study team.

Debriefing will involve an e-mail sent after immediate completion of the final follow-up. It will thank participants for their help with the study and provide them with a contact e-mail for further information.

Withdrawal of participants

Participants will be informed that they may withdraw from the study at any time without giving a reason. Unless they withdraw consent, they will be followed up irrespective of smoking outcome or protocol violation. On the basis of the intention-to-treat principle, those who do not respond to endpoint follow-up attempts will be retained in the analyses. Their outcomes will be imputed using multiple imputation (and classified as non-medication users and continuing smokers in a sensitivity analysis). Participants who indicate that they no longer wish to take part in the study will be excluded from the analyses.

Analyses

Primary analyses: Medication use

The primary two comparisons will be as follows:

- Any versus no specific medication recommendation: The first primary analysis will compare the combined medication recommendation arms (varenicline and cytisine) to the control arm (no specific medication recommendation). This analysis will assess whether recommending any medication (varenicline or cytisine) increases medication use.
- Cytisine versus Varenicline recommendation: The second primary analysis
 will compare the cytisine recommendation arm to the varenicline
 recommendation arm among participants randomised to receive a
 medication recommendation. This analysis will determine if there is a
 difference in medication use between the two recommended
 medications.

Logistic regression will be used to model the binary outcome of medication use (yes/no), adjusting for covariates (sociodemographic and smoking-related characteristics at baseline). P-values will be calculated using Wald's test.

The models will include the treatment arms as predictors. To obtain marginal risk ratios (RR) and risk differences (RD) alongside 95% confidence intervals, we will use the *marginaleffects* package in R.

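### The only stated route back to the normal app is to opt out of the study, and people who leave are excluded from the analyses, against the protocol's own intention-to-treat and follow-up rules

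*Protocol*

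**What the plan says.** Four places in the protocol bear on this.

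- **Interventions, closing paragraph.** Once enrolled, participants find the app restricted: "they will only be able to access it through the unique link based on their group allocation". The next sentence is "If participants opt out of the study, they will regain normal access to the Smoke Free app". No other way of leaving the allocated version is described.
- **Withdrawal of participants.** Follow-up is meant to be robust: "Unless they withdraw consent, they will be followed up irrespective of smoking outcome or protocol violation". Non-responders are kept and imputed: "those who do not respond to endpoint follow-up attempts will be retained in the analyses". The section ends with a different rule for leavers: "Participants who indicate that they no longer wish to take part in the study will be excluded from the analyses".
- **Outcomes, intention-to-treat statement.** All participants are analysed in their assigned group, "regardless of whether they completed the study or adhered to the intervention".
- **Sample size.** Control use of 10% is assumed against 16.8% with a recommendation (risk ratio 1.68). Recruitment runs until at least 876 participants have given primary outcome data. No opt-out rate is stated for any arm.

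**The concern.** Stopping the allocated app version is a departure from the intervention. Leaving the study ends data collection. The protocol's general rules keep the two apart, because a non-adherer stays in follow-up and in the analysis. The app-access rule joins them, because a participant who wants the normal app back is offered only the study exit. The exclusion rule then removes that person from the analysis set.

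The primary outcome is medication use, the arms differ in what they say about medication, and participants know their allocation. If the wish to leave the allocated version is related to interest in medication and differs between arms, the people removed after randomisation are not a random subset. The comparison of any recommendation with control then loses part of the protection that randomisation gave it. No later analysis can recover outcomes that were not collected.

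**Working it through.** **1. The rules side by side**

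| Participant | Followed up? | In the analysis? |
|---|---|---|
| Stops using the app, does not opt out | Yes (Withdrawal) | Yes |
| Does not answer follow-up | Attempts made | Yes, imputed; non-user in the sensitivity analysis |
| Opts out to regain the normal app | No further follow-up is described | No, if treated as no longer wishing to take part |

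The third row is the problem. The intention-to-treat statement covers every participant whether or not the study was completed, while the last sentence of the Withdrawal section removes some of them. Both cannot hold. Multiple imputation and the missing-as-non-user analysis act on missing outcomes among people kept in the analysis, so neither reaches someone excluded from it.

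**2. The plan's own figure**

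With the arcsine effect size used by the named R package, h = |2·arcsin√0.10 − 2·arcsin√0.168| ≈ 0.201. At a 2:1 ratio, control n = 1.5 × ((1.960 + 0.842)/h)² = 291.01. This rounds up to 292 per arm, or 876 in total, with 80.1% power. The stated 876 is reproduced. It counts people with outcome data and recruitment continues until it is reached, so opting out does not reduce the planned number. The issue is bias, not power.

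**3. Illustration of bias (opt-out rates are assumptions)**

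Take true use of 10% in control and 16.8% with a recommendation. Let a share w of controls opt out and be excluded, let a proportion u of them use medication, and let nobody opt out in the other arms.

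Observed control rate = (0.10 − w·u)/(1 − w); apparent RR = 0.168 / observed rate.

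| w | u | Observed control rate | Apparent RR | Would-be users lost (w·u/0.10) |
|---|---|---|---|---|
| 5% | 10% | 0.095/0.95 = 10.0% | 1.68 | 5% |
| 5% | 20% | 0.090/0.95 = 9.5% | 1.77 | 10% |
| 5% | 40% | 0.080/0.95 = 8.4% | 2.00 | 20% |
| 10% | 40% | 0.060/0.90 = 6.7% | 2.52 | 40% |

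The first row is the no-bias case: opt-outs use medication at the arm's average rate. The last row is extreme, since it needs four in ten would-be users in control to leave.

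**4. The same idea with no true effect**

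If 20% of would-be users and 5% of non-users in control opt out, the observed control rate is 0.10×0.80/(0.10×0.80 + 0.90×0.95) = 0.080/0.935 = 8.6%. A true RR of 1.68 then appears as 1.96. With 10% use in every arm, the RR appears as 1.17. With 876 completers split 279 (876×0.935/2.935) to 597, the pooled normal approximation rejects 9.8% of the time instead of 5%.

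**5. The opposite direction**

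Apply w = 5% and u = 40% to the recommendation arms instead. Their observed rate becomes (0.168 − 0.020)/0.95 = 15.6%, and the RR becomes 0.156/0.10 = 1.56, below the true 1.68. The sign depends on who leaves, and the documents do not say.

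**The case against.** A reader might infer that controls who want medication help will be the ones to leave, so that the effect will be overstated. The Rationale lists recommendations on medication among the normal app's features, and the control arm is described as receiving routine behavioural support without a specific medication recommendation. The documents do not support going that far:

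- Nowhere does the protocol say that medication content is removed from the control version. The restriction may concern the access route and not the content.
- A control participant can seek medication elsewhere without opting out, and someone who merely stops using the app is still followed.
- Vouchers reward staying: £10 at two months, £5 more for a prompt reply, and £5 at seven months.
- Participants in a recommendation arm may also want the normal app, for example to read about other options.

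All of this stands, and it removes any claim about direction or size. It can also be said that consent pages are not in the text at hand and might let people stop the app but stay in follow-up. That is possible. It would not settle the conflict in the protocol body between the exclusion of leavers and the intention-to-treat statement. Finally, restricting access limits contamination and is a defensible design choice. The restriction is not disputed here; the objection is to tying its removal to exit from the study and the analysis.

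**Conclusion.** The point holds as a structural defect and an internal contradiction. A change of app version can take a randomised participant out of follow-up and out of the analysis, against the intention-to-treat statement and against the intent to follow people despite protocol violations. This rests on reading an opt-out as the same thing as no longer wishing to take part. The protocol does not define the term, but no other rule covers such a person.

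Whether bias follows is conditional: opting out must differ by arm and be related to medication use. Under assumed control-only opt-out of 5%, with 20% to 40% of those people using medication, RR 1.68 would appear as 1.77 to 2.00. These figures show sensitivity and are not a forecast. With opting out unrelated to medication use, the RR is unchanged. The planned 876 is unaffected. The change is worth making because it is cheap and the lost outcomes cannot be recovered afterwards.

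**What to change.** In the Interventions and Withdrawal sections, treat leaving the allocated app version and withdrawing from follow-up as two separate steps.

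- When a participant opts out and regains normal access, ask whether they still agree to the 2-month and 7-month questionnaires, with the same vouchers. End follow-up only if they explicitly refuse further contact.
- Replace the exclusion sentence. Keep all such participants in the analysis as randomised and handle their missing outcomes like other missing data, unless they withdraw consent to the use of their data.
- Record the date of each opt-out and each refusal, and report both by arm.

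The cost is one added question at opt-out, matching participant information, and logged dates. A few participants with normal-app exposure would stay in the analysis, which may dilute the contrast slightly. That exposure already occurs under the current rule; the change is that these people are counted. The normal app need not be offered to anyone who has not asked to leave.

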We will also address the following secondary research questions: How effective is the intervention (advice to use either cytisine or varenicline) in promoting:

- (i) Continuous abstinence over the past month, assessed two months after enrolment?
- (ii) Biochemically verified continuous smoking abstinence for the past six months, assessed seven months after enrolment by a) group allocation (cytisine vs varenicline vs control) and b) by use of recommended medication among those in the intervention arms?

Methods

Study design

This will be a three-arm individually randomised controlled effectiveness trial.

Participants

Participants will be adult smokers residing in the UK who have downloaded and signed up to the Smoke Free app within the past week during the recruitment period. They must be intending to quit smoking in the next month, willing to participate in a 7-month study, be able to provide consent and meet all of the inclusion criteria and none of the exclusion criteria.

Inclusion criteria are:

- (i) aged between 18 and 65 years old (as cytisine is available for prescription in UK to adults 18-65 years old),
- (ii) able to consent,
- (iii) residing in UK,
- (iv) English speaking,
- (v) current cigarette smoker,
- (vi) willing to be followed up by email and complete online questionnaires after two and seven months,
- (vii) interested in making a guit attempt within the next month,
- (viii) have downloaded and signed up to the Smoke Free app within the past week during the recruitment period and have set a quit date no more than 30 days in the future.

Exclusion criteria are:

- (i) current enrolment in another smoking cessation programme/study,
- (ii) current use of smoking cessation medication,
- (iii) varenicline and/or cytisine use in the previous 12 months,
- (iv) pregnant/breastfeeding/planning to get pregnant,
- (v) self-reported moderate/severe renal impairment,
- (vi) treatment for active/latent tuberculosis,
- (vii) experience of a heart attack, stroke or severe angina within the previous two weeks,
- (viii) uncontrolled high blood pressure (> 150 mmHg systolic, > 100 mmHg diastolic),
- (ix) history of seizures.

Eligibility will be assessed via screening questions embedded in the baseline questionnaire. Those who do not meet the inclusion criteria will be provided with information about the best ways to stop smoking (6).

Sample size

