To account for missing outcome and covariate data, we will use multiple imputation with chained equations (in *mice* package). Imputation models will include experimental group, covariates, self-reported abstinence, and biochemically-validated abstinence. We will assume data are missing at random (MAR), meaning that having missing data on a variable does not depend on the true value of the variable, after accounting for predictor variables included in the imputation model. If less than 10% of data are missing, we will create 5 sets of imputations; otherwise, we will create 20 sets of imputations. Each set will be analysed separately and estimates combined using Rubin's rule.

Secondary analysis: Smoking abstinence outcomes

Above analyses will be repeated for smoking cessation outcomes, defined above in the measures section. As with the primary outcome, multiple imputation using chained equations (the *mice* package in R) will be used to account for missing outcome and covariate data.

Smoking cessation data are often missing not at random, as people who relapse to smoking are generally less likely to complete follow-up. However, the usual way to account for missing not at random, assuming "missing=smoking" (where all individuals with missing follow-up data are assumed to have relapsed to smoking), has been shown to be too extreme in internet-based smoking cessation trials (28). Instead, sensitivity analyses will examine the degree to which violations in the MAR assumption affect results. Multiple imputation with delta-adjustment will be used, with the degree of adjustment ranging from none (delta=0; MAR analysis) to very large (delta=100, approximating the missing=smoking assumption).

	Simple unadjusted complete case and "missing=smoking" analyses will be included in supplementary files as these are often used in meta-analysis.					
	Cost effectiveness					
	First, we will use the smoking cessation outcome directly observed in this trial—comparing the proportion of participants who report having quit smoking across trial arms at follow-up. This will provide a trial-based estimate of the intervention's impact on quitting, which can be used to estimate the potential health benefits (e.g., quality-adjusted life years [QALYs] gained) associated with the intervention.					

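### A 2-month report of smoking inside the 6-month abstinence window does not settle the 7-month outcome, so a participant who has already reported failing it can be counted or imputed as abstinent

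*Protocol*

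**What the plan says.** All references are to the Protocol; no SAP was available.

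- **6-month outcome (Measures, Outcomes, secondary outcome ii).** "self-reported abstinence will be measured as not having smoked more than five cigarettes for the entire 6-month period preceding the 7-month follow-up".
- **2-month outcome.** Research questions: "Continuous abstinence over the past month, assessed two months after enrolment". Measures repeats it as "continuous abstinence for one month assessed at 2-month follow-up". Neither place gives a cigarette allowance. Table 1 schedules sustained abstinence at both follow-ups.
- **Classification.** Under Procedure, "Participants who report 6-month continuous abstinence at the 7-month follow-up will be asked to measure their CO levels". Under Measures, "those with a CO reading of less than 8 parts per million will be classified as abstinent". Neither sentence refers to the 2-month answer.
- **Missing outcomes.** "Multiple imputation will be used to account for missing outcome data", with missing described as "participants who will be lost to follow-up or did not provide outcome data". Withdrawal of participants repeats the rule for endpoint non-responders. No exception is made for a failure already reported.
- **Imputation model (Analyses).** Self-reported abstinence is listed as a model variable, without a time point.
- **Short replies (Procedure).** By single click, text or call, participants can give medication use only at 2 months and 6-month abstinence only at 7 months.

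**The concern.** The two windows overlap, so the trial may already hold the answer to the 6-month question for some participants when they reach month 7. Three records show what the stated rules do:

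- **Record A.** Reports at month 2 smoking daily, quits in month 3, claims six months' abstinence at month 7, and has a CO reading below 8 ppm. The rules count verified abstinence; the outcome definition says failure. A CO reading at about month 7 cannot reveal smoking in month 2.
- **Record B.** Reports at month 2 smoking daily and gives no 7-month answer. The rules send this participant to imputation, where abstinence can be drawn; by definition the outcome is a known failure.
- **Record C.** Abstinent at month 2 and missing at month 7. The outcome is truly unknown, and imputation is appropriate.

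This is the trial's only biochemically verified cessation outcome. False successes raise its rate and, if equally common in all arms, pull the risk ratio towards 1. Imputing Record B also discards outcome information already collected, in a setting where the protocol itself expects that "people who relapse to smoking are generally less likely to complete follow-up".

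**Working it through.** **Plan's own figure.** The protocol states no sample size or rate for abstinence. Its only figure is 876 (292 per arm), for medication use. It reproduces with the arcsine method: h = 2·asin(√0.168) − 2·asin(√0.10) = 0.2011; control n = 1.5 × (1.960 + 0.842)² / 0.2011² = 291.01, rounded up to 292; 3 × 292 = 876. Nothing below changes it.

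**Windows.** Let t2 and t7 be the reply times in months. The 2-month item covers t2 − 1 to t2; the 7-month item covers t7 − 6 to t7. The first lies wholly inside the second when t2 − 1 ≥ t7 − 6, that is, t7 − t2 ≤ 5. On schedule, 7 − 2 = 5, so the windows nest exactly, with no slack. A 7-month reply delayed by d days more than the 2-month reply leaves the first d days of the 2-month window outside. A late 2-month reply alone keeps the windows nested.

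**Counts per arm (assumed rates, none from the documents).** Take 292 per arm, all giving a 2-month abstinence answer; f = share reporting smoking beyond the allowance, 0.6 to 0.8; m = share of those missing at month 7, 0.3 to 0.5; c = share of the rest who claim six months and pass CO, 0.01 to 0.05. Imputation is assumed to draw abstinence at rate c.

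- Contradicted claims counted: 292·f·(1 − m)·c, from 292 × 0.6 × 0.5 × 0.01 = 0.9 to 292 × 0.8 × 0.7 × 0.05 = 8.2.
- Reported failures imputed abstinent: 292·f·m·c, from 292 × 0.6 × 0.3 × 0.01 = 0.5 to 292 × 0.8 × 0.5 × 0.05 = 5.8.
- Together: f·c, from 0.6% to 4.0% of the arm.

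**Does the imputation model already solve it?** Assume 876 participants; 25% abstinent at month 2, of whom 32% succeed (true rate 0.25 × 0.32 = 8%); 7-month data missing in 30% of those abstinent at month 2 and 50% of the others. Reported failures missing at month 7 number 876 × 0.75 × 0.5 = 328.5.

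- *2-month abstinence not a predictor, no contradicted claims.* The observed success rate is (0.25 × 0.7 × 0.32) / (0.25 × 0.7 + 0.75 × 0.5) = 0.056 / 0.55 = 10.2%, so 328.5 × 0.102 ≈ 33 are imputed abstinent. With c of 2% or 5% this becomes about 38 or 45.
- *2-month abstinence a predictor.* The expected count is 328.5·c: close to 0 with no contradicted claims, 6.6 at c = 2% and 16.4 at c = 5%. Contradicted claims left in the data teach the model that month-2 smokers can succeed.

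A simulation on the same assumptions gave 33, 38 and 46 without the predictor and 0.5, 7 and 16 with it. A second simulation used other assumptions: 1,460 randomised, 60% response at month 2, and 60% (abstainers) and 40% (others) at month 7. There, 17% of known failures were imputed abstinent without the predictor and 1.4% with it. Adding the coding rule to the predictor moved the overall rate only from 14.9% to 14.6%. The remaining gap to the true 10.9% came from the assumed not-at-random response.

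**What can be recovered.** If 2–6% of participants quit after month 2 and 25–50% of them claim six months, the inflation is 0.02 × 0.25 = 0.5 points to 0.06 × 0.5 = 3 points. Only those with a 2-month abstinence answer can be corrected: at 60% response, 0.3 to 1.8 points.

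**Effect on the comparison if false successes are equal across groups.** With assumed true rates of 6% and 10% (292 v 584), adding e to both leaves the risk difference at 4 points. The risk ratio (10 + e)/(6 + e) falls from 1.67 to 1.57 at e = 1 and 1.40 at e = 4; power falls from 51% to 47% and 38%.

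**The case against.** The strongest reply is that the protocol defines the outcome over the whole six months, a definition Record A fails, and that resolving contradictory answers belongs in the SAP. This stands only in part. The protocol does not merely stay silent: it states a classification rule and an imputation rule, and applied literally both can conflict with its own definition.

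The other replies carry weight:

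- **Threshold.** A reader might infer that every 2-month answer of not abstinent is a known failure. The documents do not support this. The five-cigarette allowance is stated for the 6-month outcome only, so such an answer could reflect one to five cigarettes.
- **Imputation.** A reader might also infer that many known failures will be imputed abstinent. That requires reading self-reported abstinence in the imputation model as excluding the 2-month item. Including it is at least as natural, since secondary outcome (i) is exactly that, and the problem then nearly vanishes unless contradicted claims occur. The missing=smoking analysis, and delta adjustment at its upper end, would also score Record B as a failure. Neither touches Record A.
- **Bias between arms.** One can imagine participants who wait for a prescription quitting late and overstating their abstinence. Nothing in the documents shows this differs by arm.
- **Late replies.** Because nesting is exact only on schedule, a rule that ignores reply dates could misclassify.
- **Reach.** Those who gave only medication use at month 2 cannot be cross-checked.

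**Conclusion.** The point holds in limited form. The 2-month abstinence report covers part of the 6-month window, and the rules as written let a participant who reported smoking beyond the allowance be counted or imputed as abstinent. Contradicted claims are the more durable part, because no planned sensitivity analysis corrects them. False imputation is probably small if 2-month abstinence is already a predictor.

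The size cannot be derived from the documents. The range of 0.6 to 4.0 points assumes that all 292 per arm answered the 2-month abstinence item, so fewer would be identifiable in practice. The wider figures in the working should not be read as estimates for this trial. What is shown is possible misclassification and, if it is equal across arms, dilution of the risk ratio; a biased treatment comparison is not shown. One secondary outcome is affected, and the primary outcome and the 876 are not. The change should be made, because it is cheap and brings the rules into line with the definition.

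**What to change.** 1. Apply the five-cigarette allowance to the 2-month abstinence item, so that a lapse of one to five cigarettes does not by itself rule out 6-month success.
2. Before imputation, code the 6-month outcome as not abstinent for anyone whose 2-month report shows more than five cigarettes within the 6-month window, whether the 7-month answer is missing or contradicts it. Judge the window by actual reply dates, using the scheduled date where there is no 7-month reply. Where the replies are more than five months apart, apply the rule only if the excess falls in the overlapping days.
3. Impute only outcomes not already fixed by an observed answer, and name 2-month abstinence explicitly as a predictor in the imputation model.
4. Report the number of contradicted claims by arm, and keep the 7-month-report-only classification as a sensitivity analysis.

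**Cost.** One definition, one coding step and one extra table row. No new visit or scheduled item is needed, though the wording of the 2-month item must carry the allowance. The reported abstinence rate may fall slightly. The check reaches only those who answered the 2-month abstinence item, so the number answering it should be shown by arm.
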